Those currently on MS disease modifying therapy will have received a stable regimen of the medications for at least 30 days prior to screening and will continue the same doses and regimens for the duration of their study participation.

Consented subjects will be assessed for relapse criteria and those who meet study eligibility criteria and agree to be treated with a standard 3 to 5 day pulse of high dose corticosteroids, will be randomized with equal probability to 1 of 2 treatment groups: placebo capsule or active Isoxsuprine (ISX).

The Screening Visit will take place within 7 days of relapse onset and within 48 hours of initiating high dose steroids. Subjects may start corticosteroids anytime during this 7 day window. During the screening period, subjects will be assessed with the Expanded Disability Status Scale (EDSS), Multiple Sclerosis Functional Composite (MSFC), and cognitive testing prior to treatment with ISX or placebo (1:1 ratio).

Safety Assessments during screening will include a physical exam, electrocardiogram, vital signs, weight and a urine pregnancy test for females of child bearing potential. At 7 (\pm 1) days following the completion of the 5-day ISX dosing, subjects will be re-assessed with the EDSS.

Subjects will be evaluated for treatment response using the EDSS and other standard measures described below at visits 1, 4 and 12 weeks.

Study drug will be administered as one (1) 10 mg capsule, 3 times daily for 5 days in conjunction with concomitant dosing with high dose corticosteroids. This can be any accepted regimen, including daily iv methylprednisolone 1000 mg/day or 600mg oral

PROTOCOL TITLE: Double-blind, placebo-controlled, randomized study of the safety and tolerability of isoxsuprine HCL combined with high dose steroid treatment of multiple sclerosis (MS) relapse

prednisone two times a day at approximately 8AM and noon, with food, as typically provided by UNM MS Specialty Clinic

4. Inclusion and Exclusion Criteria

Inclusion Criteria

Subjects must meet all the following criteria for inclusion in the study at the Screening Visit:

1. Subjects must be adequately informed and understand the nature and risks of the study and must be able to provide a signature and date on the ICF;
2. Male or female subjects between 18 and 50 years of age, inclusive;
3. Confirmed diagnosis of Multiple Sclerosis or Clinically Isolated Syndrome (CIS) suggestive of MS, according to the 2010 Revised McDonald criteria.

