15. Inability to swallow oral capsules, or a history of gastrointestinal malabsorption that would preclude the use of oral medication;
16. If female, is pregnant or lactating;
17. History of hypersensitivity or allergic reaction to any of the study drugs.
18. History of heavy use of tobacco/smoking

5. Number of Subjects

Approximate Number of Subjects

Target enrollment is 20 subjects equally randomized to ISX or matching placebo.

6. Study Timelines

Approximate Duration of Subject Participation

Subjects will participate in the study for a total of up to 12 weeks. Study visits include a screening/randomization visit with drug administered and safety and efficacy assessment visits at weeks 1 (7 days after completion of ISX dosing), 4 and 12 weeks.

7. Study Endpoints

Primary safety endpoints will be assessed using the following:

- Individual GI symptoms
- Adverse events (AEs)
- Vital signs (temperature, respiratory rate, pulse, systolic and diastolic blood pressure)
- Electrocardiogram (ECG) parameters (heart rate, RR, QT, QTcF, QTcB, PR, and QRS intervals)

Secondary efficacy endpoints will be assessed using the following:

- Kurtzke Expanded Disability Status Scale (EDSS0)
- Timed 25-foot Walk (25FTW)
- Symbol Digit Modality Test (SDMT)

8. Research Setting

PROTOCOL TITLE: Double-blind, placebo-controlled, randomized study of the safety and tolerability of isoxsuprine HCL combined with high dose steroid treatment of multiple sclerosis (MS) relapse

Aside from recruitment which will take place at the Clinical Neuroscience Center, MS Clinic, all research activities will be completed at the MS Specialty Clinic. The MS Specialty Clinic is located at [name].

9. Prior Approvals

The following approvals are available and will be provided with study documentation:

- Departmental Review Form
- Drug Attachment for Isoxsuprine and matching placebo
- IND Exemption Checklist

10. Study Procedures

Screening Visit (Visit 1) Procedures/Assessments

The following procedures will be performed at the Screening Visit:

- Informed consent.
- Inclusion/exclusion criteria.
- Medical and surgical history.
- Demographics.
- Physical examination.
- EDSS.
- Multiple Sclerosis Functional Composite (MSFC).
- Cognitive Battery consisting of the Symbol Digit Modality test
- Height and Weight.
- Vital signs.
- Urine pregnancy test.
- Electrocardiogram (ECG) pre-dose.

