- Treat with oral prednisone (600 mg BID) if not already receiving corticosteroid pulse, which can be via Iv or Po route.
- Adverse events and concomitant medications.

Randomization Visit (Visit 1) Procedures/Assessments

- Initiate treatment with Isoxsuprine HCL (oral) Capsule 10mg or placebo.
- 1 hour monitoring post dose.
- Vital signs.
- Electrocardiogram (ECG) post dose.
- Adverse events.

1 Week Post Treatment Safety Follow-Up Visit (Visit 2) Procedures/Assessments

The following procedures will be performed at this visit:

- Physical examination.
- EDSS.

PROTOCOL TITLE: Double-blind, placebo-controlled, randomized study of the safety and tolerability of isoxsuprine HCL combined with high dose steroid treatment of multiple sclerosis (MS) relapse

- Multiple Sclerosis Functional Composite (MSFC).
- Vital signs.
- Adverse events and concomitant medications.

4 Week Post Treatment Safety Follow-Up Visit (Visit 3) Procedures/Assessments

The following procedures will be performed at this visit:

- Physical examination.
- EDSS.
- Multiple Sclerosis Functional Composite (MSFC).
- Cognitive Battery (Symbol Digit Modality).
- Vital signs.
- Adverse events and concomitant medications.

12 Week Post Treatment Safety Follow-Up Visit (Visit 4) Procedures/Assessments

The following procedures will be performed at this visit:

- Physical examination.
- EDSS.
- Multiple Sclerosis Functional Composite (MSFC).
- Cognitive Battery (Symbol Digit Modality).
- Vital signs.
- Adverse events and concomitant medications.

Adverse Events

Adverse events will be recorded from signing of the ICF and followed by the investigator until the AE is resolved or stabilized. Any and all safety measures (which includes standard of care activities) should be provided by the study site to the subject. Any study site follow-up should be documented.

Medical History

Medical history will be obtained at the Screening Visit. Medical history will include a review of the following systems: general medical and surgical history. Historical and current medical conditions including date of last menstrual period for female subjects will be recorded.

Current Medical Conditions

At each visit after screening, subjects will be asked about any changes in medical conditions, specifically new medical conditions and worsening of existing medical conditions. Any changes since the Screening Visit will be recorded as AEs, as appropriate.

Physical Examination

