The medication should be kept at room temperature and will be labeled according to all applicable national and local regulations.

The following treatments will be administered:

- Treatment A: Isoxsuprine HCL 1 Capsule 3 times daily for 5 consecutive days,
OR
- Treatment B: Placebo 1 Capsule 3 times daily for 5 consecutive days.

The subject or clinic staff will administer the first dose of drug in the clinic under the supervision of study staff. The subject will remain in the clinic for at least 1 hour post-dose to monitor for allergic or adverse reactions. Thereafter, all doses will be administered by the subject or the subject's caregiver at home.

Subject Unblinding

The identity of the treatment assigned to individual subjects can be revealed in an emergency only. A subject's treatment assignment should only be unblinded when knowledge of the treatment is essential for the safety of the subject

Storage of Clinical Supplies

Ioxsuprine HCL and placebo will be maintained in a temperature controlled, secure locked area with restricted access at the study site pharmacy.

Drug Accountability

Subjects will be asked to return all empty study medication containers at study visit week 1 (Visit 2). They will be asked if all study medication was taken as directed.

Safety Assessments and Procedures

The following safety assessments will be evaluated (see section 10): AEs, physical examinations, ECGs, vitals, weight, urine pregnancy tests and Concomitant Medications.

PROTOCOL TITLE: Double-blind, placebo-controlled, randomized study of the safety and tolerability of isoxsuprine HCL combined with high dose steroid treatment of multiple sclerosis (MS) relapse

[name] and [name] to serve as a Data Safety Monitoring Board. They will have no connection to the study. On a quarterly basis, study progress and data will be submitted for review. Adverse events will be reported to the DSMB and IRB within 7 days and Serious Adverse Events within 24 hours. The DSMB will help ensure patients safety and rights though out the study. The DSMB will have authority to provide recommendations on the conduct of the study, such as suspension of the study or advise on any potential protocol revisions.

IND Waiver Justification

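### A primary safety endpoint, individual GI symptoms, has no assessment of its own and no scheduled enquiry while 14 of 15 doses are taken; the 1-week ECG is scheduled in one place and left out in another

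*Protocol*

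**What the plan says.** **Endpoint.** Protocol Section 7 opens its list of primary safety endpoints with "Individual GI symptoms". Adverse events, vital signs and ECG parameters follow as separate items.

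**Collection.** None of the visit lists in Section 10 has a GI item. The list under Safety Assessments and Procedures in Section 26, which refers back to Section 10, has none either. Two general routes remain, both in Section 10:
- "Adverse events will be recorded from signing of the ICF and followed by the investigator until the AE is resolved or stabilized"; adverse events also appear in every visit list.
- "At each visit after screening, subjects will be asked about any changes in medical conditions", meaning new conditions or worsening of existing ones.

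**Exposure.** Section 3 gives one capsule three times daily for 5 days. Section 26 (Dosing Procedures) places the first dose in the clinic: "The subject will remain in the clinic for at least 1 hour post-dose to monitor for allergic or adverse reactions". It continues: "Thereafter, all doses will be administered by the subject" or a caregiver, at home.

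**Next contact.** Section 6 schedules "safety and efficacy assessment visits at weeks 1 (7 days after completion of ISX dosing), 4 and 12 weeks". Section 3 gives the first of these a window, at 7 (±1) "days following the completion of the 5-day ISX dosing, subjects will be re-assessed with the EDSS". At that visit empty containers come back and, under Drug Accountability in Section 26, "They will be asked if all study medication was taken as directed". That question is about doses, not symptoms.

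**ECG.** The Electrocardiogram subsection of Section 10 places a 12-lead ECG at baseline (before and after the dose at Visit 1) and at 1 week. The Visit 2 list in the same section names physical examination, EDSS, MSFC, vital signs, adverse events and concomitant medications, but no ECG.

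**The concern.** Safety and tolerability are the primary objective, and Section 11 itself names nausea, vomiting and abdominal distress among the effects reported, on rare occasion, with oral isoxsuprine. An endpoint listed apart from adverse events implies data beyond the adverse-event log, yet the protocol provides no procedure to collect them. Either the item duplicates adverse events or its procedure is missing.

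The timing adds to the problem. Nobody is scheduled to ask about symptoms during the days when drug-related GI effects would be expected. The first structured question comes about a week after the last capsule, when mild, self-limited nausea is easily forgotten. An analysis plan can tabulate GI terms from what was reported, but it cannot create reports that were never elicited. Section 15 says these pilot data may support a larger efficacy study, so a quiet tolerability table could be read as reassurance when it partly reflects little observation.

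The ECG discrepancy is of another kind. Staff who follow the visit list and staff who follow the subsection would collect different data on a primary endpoint.

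**Working it through.** The protocol states no figure for this point that could be reproduced. The check is a count from the schedule.

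**Inputs**
- 3 doses a day for 5 days (Section 3).
- First dose in clinic, all others at home (Section 26).
- Visit 2 at 7 (±1) days after dosing ends (Section 3).
- 20 subjects, equally randomized (Section 5).

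**Doses without scheduled contact**
- Total: 3 × 5 = 15.
- At home: 15 − 1 = 14, and 14/15 = 93%.

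**Recall interval at Visit 2**, counting the first dose as day 1 and assuming the last dose falls on day 5:
- Visit 2: day 5 + 7 (±1) = day 11 to 13.
- Symptom on day 5: 11 − 5 = 6 to 13 − 5 = 8 days.
- Symptom on day 1 after leaving the clinic: 11 − 1 = 10 to 13 − 1 = 12 days.
- Overall: 6 to 12 days.

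If the first dose is given late enough on day 1 for the fifteenth to fall on day 6, Visit 2 moves to day 12 to 14. A day-6 symptom is then 6 to 8 days old and a day-1 symptom 11 to 13, an overall range of 6 to 13 days.

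**Weight of one unreported subject**
- Per arm: 20 / 2 = 10.
- One affected subject not reported: 1/10 = 10 percentage points off that arm's rate.
- If both arms lose the same fraction m of affected subjects, the expected difference in reported rates is (1 − m) times the true difference. Equal loss therefore makes both arms look better and shrinks any contrast.

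**GI assessments in the schedule**
- Dedicated items in the Section 10 visit lists: 0.
- Dedicated items in the Section 26 safety list: 0.

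**ECG per subject**

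| Source in Section 10 | Visit 1 pre-dose | Visit 1 post-dose | Visit 2 | Total |
|---|---|---|---|---|
| Visit lists | 1 | 1 | 0 | 2 |
| Electrocardiogram subsection | 1 | 1 | 1 | 3 |

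Over 20 subjects this is 20 × 2 = 40 or 20 × 3 = 60 tracings, a difference of 20. The disputed tracing would be taken off drug on either reading of the visit timing.

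**The case against.** The best defence is that Section 7 names what will be assessed and does not promise an instrument. Adverse events are recorded from consent, subjects are asked about changes at every later visit, and the abdomen is part of the physical examination at all four visits. GI terms can be extracted from the adverse-event log, and a form not shown here might carry a GI prompt. Section 17 encourages questions by telephone, and Section 26 requires adverse events to reach the monitoring board and the IRB within 7 days. In a 20-subject pilot, recall at about a week is a defensible choice, and the 10-point figure is only 1/10. It does not show that any event would be missed.

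Much of this stands, and it sets the limits of the point. It does not remove the gap. An invitation to telephone is not a scheduled enquiry, reporting deadlines apply only once an event is known, and the protocol still does not say where a separately listed primary endpoint comes from.

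A reader might go further in three ways that the text does not support.
- *GI symptoms are not collected at all.* They are, through general adverse-event recording.
- *The Visit 1 vital signs cannot be placed relative to the dose.* Section 10 requires date and time for all vital signs. The randomization list runs from starting treatment through 1 hour of monitoring to vital signs and the post-dose ECG, which points to a post-dose reading.
- *Visits 2 to 4 pass for on-treatment data.* Section 10 already titles them post-treatment safety follow-up.

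**Conclusion.** The point holds for the GI endpoint and for the ECG schedule. One primary safety endpoint has no assessment of its own. Home symptoms over 14 of 15 doses rest on spontaneous report or on recall of about 6 to 12 days (up to 13 if dosing runs into a sixth day). One unreported subject is worth 10 percentage points in an arm of 10. The amount of under-reporting is unknown, and under blinding nothing in the protocol suggests that it would differ between arms. The 1-week ECG is a plain contradiction affecting one tracing per subject on a primary endpoint; it is small because that tracing is off drug.

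Both parts should be fixed. Neither makes the trial unworkable. The conclusion assumes that no case report form, which is not available here, supplies a dedicated GI prompt. Even if one did, the gap in enquiry during dosing would remain.

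As a minor note, scheduled on-drug vital signs and ECG are confined to the first dose. A reader might infer that the absence of readings on dosing days 2 to 5 is an error. It is a design choice, and on-drug conclusions from those measures should simply be confined to the first dose as well.

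**What to change.** 1. **GI endpoint.** Add to Section 10 a one-page card on which the subject records individual GI symptoms and any other adverse events on each of the 5 dosing days, returned with the containers at Visit 2. Name the card in Section 7 as the source of the GI endpoint. Allow a sixth row if dosing can run into a sixth calendar day.
2. **ECG.** Reconcile the Electrocardiogram subsection with the Visit 2 list, so that Section 10 gives one answer on whether an ECG is taken at Visit 2.

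**Cost.** The card means 20 sheets and 20 × 5 = 100 daily rows of data entry (20 × 6 = 120 with a sixth row), a database form and an ethics amendment, which can also carry the ECG wording. It adds no visit and no subjects. The documents do not give the staff time. The burden on subjects is slight. Daily prompting will probably raise reported GI rates in both arms, so the rates will not be comparable with spontaneous-report rates elsewhere. The comparison within the trial is unaffected, because both arms use the same card. The card does not supply on-drug vital signs or ECGs for days 2 to 5.

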25. Consent Process	13
26. Documentation of Consent	16
27. Study Test Results/Incidental Findings	16
28. Sharing Study Progress or Results with Subjects	17
29. Inclusion of Vulnerable Populations	18
30. Community-Based Participatory Research	19
31. Research Involving American Indian/Native Populations	19
32. Transnational Research	19
33. Drugs or Devices	20
Checklist Section	21
34. Export Control	22

PROTOCOL TITLE: Double-blind, placebo-controlled, randomized study of the safety and tolerability of isoxsuprine HCL combined with high dose steroid treatment of multiple sclerosis (MS) relapse

1. Objectives

Primary Objective

The primary objective of this study is to:

- Assess the safety and tolerability of Isoxuprine (ISX) in combination with high dose corticosteroids in subjects experiencing acute relapses due to multiple sclerosis.

The safety analysis population will include all randomized subjects who receive at least one dose of study drug. Safety endpoints will be summarized by treatment group (ISX or placebo) from the time of the first dose and include all available safety data. No formal statistical testing will be done. All adverse event data will be listed and will be summarized by treatment group. Quantitative safety variables (vital signs) will be summarized at each visit by treatment group and changes from baseline will be summarized by treatment group at selected visits.

Secondary Objective

The secondary objective of this study is to:

- Evaluate the potential efficacy of Isoxuprine as add-on treatment for improving neurological deficits in walking ability, visual acuity, and other associated symptoms of MS, including fatigue and cognitive dysfunction in this MS population experiencing a relapse.

The efficacy analyses will include all randomized and dosed subjects who provide Week 12 efficacy data. The key secondary analysis will compare the changes in EDSS functional system scores most relevant to the relapse associated disability (e.g. pyramidal, visual, cerebellar). Also walking speed and z-score from the Multiple Sclerosis Functional composite score (MSFC) from Baseline to Week 12 in the ISX group compared to the placebo group.

2. Background

Overview

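### Drug Accountability asks only for empty containers and no capsule count, so how much of the 5-day course was taken rests on self-report

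*Protocol*

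**What the plan says.** Section 3 (Study Design) sets the regimen: "Study drug will be administered as one (1) 10 mg capsule, 3 times daily for 5 days". Section 26 (Dosing Procedures) has one supervised dose: "The subject or clinic staff will administer the first dose of drug in the clinic under the supervision of study staff". After that: "Thereafter, all doses will be administered by the subject or the subject's caregiver at home".

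Section 26 (Drug Accountability) then gives the whole of the exposure check in two sentences. The first is "Subjects will be asked to return all empty study medication containers at study visit week 1 (Visit 2"). The second is "They will be asked if all study medication was taken as directed".

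Visit 2 is timed in Section 3 at 7 (±1) "days following the completion of the 5-day ISX dosing, subjects will be re-assessed with the EDSS". The primary objective in Section 1 is to "Assess the safety and tolerability of Isoxuprine (ISX) in combination with high dose corticosteroids in subjects experiencing acute relapses due to multiple sclerosis".

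**The concern.** The return request names the less informative object. A subject who finished the course has an empty container and is asked for it. A subject who missed or stopped doses has capsules left over, and the sentence as written does not ask for that container. No count is specified for anyone.

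Tolerability is part of the primary objective, and Section 11 (Treatment Discontinuation) foresees that study drug will sometimes be stopped for adverse effects. Whether subjects could complete a 5-day course is a natural thing to report from such a trial. If the number of doses taken is not recorded at Visit 2, no later analysis plan can recover it. The gap is therefore one of data collection and cannot be left to the SAP.

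**Working it through.** The protocol gives no adherence or exposure figure, so there is none to reproduce. The check has three parts.

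**1. Does any other section supply the count?**

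- Section 10, Visit 2 list: physical examination, EDSS, MSFC, vital signs, adverse events and concomitant medications. It has no capsule count, diary or dosing record.
- Section 11, Subject Withdrawal: the reason for discontinuation is recorded. No stop date or number of doses is mentioned. The sentence concerns leaving the study, so it may not cover a subject who stops the drug but stays in follow-up.
- Section 11, Treatment Discontinuation: lists events that lead to stopping study drug, with no instruction to record the doses taken.

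None closes the gap.

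**2. How much of the exposure is affected?**

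- Doses per subject: 3 per day × 5 days = 15.
- Supervised: 1. At home: 15 − 1 = 14, and 14/15 = 93%.
- Subjects per arm: 20/2 = 10 (Section 5, equal randomisation).
- Interval from last dose to the adherence question, taking Visit 2 as 7 ± 1 days after the scheduled end of dosing: 6 to 8 days for a completer. For a subject whose last dose was on day *d*, it is (5 − *d*) + 6 to (5 − *d*) + 8 days, so 10 to 12 days if *d* = 1.

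**3. What does one misclassified subject do to a completion rate?**

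- Shift: 1/10 = 10 percentage points.
- Exact (Clopper–Pearson) 95% interval for the proportion stopping early:
  - 0/10: 0 to 1 − 0.025^(1/10) = 0 to 30.8%.
  - 1/10: 0.3% to 44.5% (lower limit 1 − 0.975^(1/10) = 0.3%; upper limit from the beta quantile).
- Chance that an arm of 10 has at least one early stopper, 1 − (1 − *p*)^10. The rates *p* are assumptions, since the protocol gives none:

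| Assumed early-stop rate | At least one in an arm of 10 |
|---|---|
| 10% | 65% |
| 20% | 89% |
| 30% | 97% |

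This table gives the chance that such a subject exists, not the chance that the subject is misclassified. The documents offer no basis for estimating the latter.

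**The case against.** The strongest reply is that no planned primary result uses a dose count. Section 7 lists the primary safety endpoints as GI symptoms, adverse events, vital signs and ECG parameters. Section 1 summarises safety by treatment group among randomised subjects with at least one dose, without formal testing. The supervised first dose verifies entry to that population. Intolerance should also show up as adverse events, which are recorded from consent and collected at every follow-up visit. All of this stands: the group summaries are unaffected, and what may be lost is the number of doses, not necessarily the tolerability signal.

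A reader might go further and infer that adherence is biased upward, or that exposure data are missing because of intolerance. The documents do not support this. The adherence question goes to every subject, early stoppers included, and the text does not bar staff from noting missed doses in the answer. A subject with no empty container to hand back would also tend to stand out. For an early stopper to be counted as a completer, that subject must report full adherence while holding leftover capsules. This is possible, but nothing in the protocol shows that it will happen.

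A reader might also multiply 14 home doses by 10 subjects and cite 140 unobserved doses in the ISX arm as the size of the flaw. That figure belongs to any home-dosed course of this length and would be the same after the fix. Nor is the weakness confined to early stoppers, since an empty container does not prove that the capsules were swallowed.

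What remains is that the rule leaves part-used containers out and asks for no count.

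**Conclusion.** The point holds in a limited form. As written, the Drug Accountability rule leaves the extent of exposure for doses 2 to 15 to self-report, and the check is weakest in subjects who missed or stopped doses. The consequence falls on any statement about completion of the 5-day course and on any reading of events against doses taken. In an arm of 10, each misclassified subject is worth 10 percentage points of completion.

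It does not bias the planned adverse event, vital sign or ECG summaries by randomised group, and it does not put the safety population in doubt. The conclusion rests on the protocol text alone. It assumes that site staff follow the request literally; in practice they may accept part-used containers, but the protocol does not ask for them. This is a worthwhile, inexpensive improvement, not a threat to the primary results.

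**What to change.** In Section 26, Drug Accountability, delete *empty*. State that subjects return all study medication containers, with any unused capsules, at Visit 2, and that staff count and record the returned capsules and the date of the last dose. Record the number dispensed as well, so that capsules taken can be derived as dispensed minus returned. Add the count to the Visit 2 list in Section 10. Summarise capsules taken and the proportion completing all 15 doses by arm, descriptively.

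The cost is a few minutes of counting at a visit already scheduled and one or two extra data fields per subject. No dose or clinical rule changes. A count shows what was not returned; it still does not prove ingestion.
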